### 9.3 POPULATIONS FOR ANALYSES

All efficacy and safety data summaries and analyses will be performed by study arm using an Intent-to-Treat (ITT) population defined as all randomized patients.

The number of patients identified as candidates will be reported, as will the number screened (i.e. consented). The number and percentage of patients randomized, patient population (ITT), and treatment status (completed, discontinued/withdrew) will be summarized both by treatment group and overall. Reasons for discontinuation/withdrawal will be presented.

An exploratory, per protocol (PP) analysis will focus on patients who use the assigned intervention on at least 50% of days during the first 30-day period. Usage meta-data on the headsets will facilitate sample definition in this population. If headset meta-data is not available, we will rely on weekly self-report usage surveys.

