#### 7.2 PARTICIPANT DISCONTINUATION/WITHDRAWAL FROM THE STUDY

Participants are free to withdraw from the study at any time upon request. Participants request to withdraw will be asked to clarify whether they wish to discontinue the intervention but still complete the periodic survey questionnaires. In this case, the participant would not be considered withdrawn.

An investigator may withdraw a participant who develops any of the exclusions criteria in section 5. The reason for participant discontinuation or withdrawal from the study will be recorded.

Subjects who signed the informed consent form, were randomized and received the study intervention, and subsequently withdraw, or are withdrawn or discontinued from the study without engaging with the VR intervention will be replaced. Participants are considered to have engaged with the VR intervention if there is any self-reported VR usage in survey questionnaires or if any metadata are recorded in a participant's headset during their possession of the VR headset.

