### 9.4 STATISTICAL ANALYSES

#### 9.4.1 GENERAL APPROACH

All statistical analyses will be performed jointly by the Cedars-Sinai Biostatistics Core and the Cedars-Sinai Center for Outcomes Research and Education (CS\_CORE) using SAS® software version 9.3 or higher (SAS Institute, Cary, NC, USA), R pack3.5.0 (R Foundation for Statistical Computing, Vienna, Austria) or Stata software version 14 or higher (StataCorp LLC, College Station, TX, USA).

Continuous variables will be summarized using descriptive statistics (N, mean, standard deviation, minimum, median, and maximum). Categorical variables will be summarized using the number and percentage of patients in each category. Data will be summarized with respect to patient demographic and baseline characteristics both across the study and by study-arm. The efficacy endpoints, safety assessments, and other outcome results for each treatment group will be summarized descriptively unless otherwise indicated. In addition, statistical model estimates of least squares means, treatment differences, p-values and 95% confidence intervals will also be provided where relevant. The fit of linear models will be assessed using residual plots and/or other diagnostic plots as appropriate. The fit of logistic models will be assessed using Hosmer-Lemeshow goodness-of-fit and/or receiver operating characteristic (ROC) curves as appropriate. All statistical tests will be 2-sided and performed at the 0.05 level of significance unless stated otherwise. Baseline is defined as the value at the screening week (Day -8 to Day -2) for all parameters, unless specified otherwise.

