#### 9.4.4 SAFETY ANALYSES

All safety analyses will be descriptive. No statistical testing will be performed.

---

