### 11.3 REVISED RECRUITMENT TARGETS

**Current and Revised Recruitment Targets:** Currently, the target sample size for the parent study is 360 participants. Regarding Hispanic participants, although we are meeting our original recruitment goal which was set at 11% to reflect U.S. Census data, there is a much higher prevalence of Hispanic/Latinx individuals in Southern California where the 2019 Los Angeles County Census revealed a 48% prevalence of this group. **We intend to implement these new recruitment materials and strategies once we have randomized 50% of the overall study cohort.** Because certain participants are eligible for replacement if they are withdrawn after randomization, this will occur at approximately **participant #200** based on current rates of withdrawal. Specifically, beginning at this point, we will seek to recruit a second-half study sample that is **17% non-Hispanic black** (previous target 12%), **40% Hispanic** (previous target 11%), and **35% non-Hispanic white** (previous target 76%).

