#### **4.2 Analysis Populations and Patient Disposition**

All efficacy and safety data summaries and analyses will be performed by study arm using an Intent-to-Treat (ITT) population defined as all randomized patients.

The number of patients identified as candidates will be reported, as will the number screened (i.e. consented). The number and percentage of patients randomized, patient population (ITT), and treatment status (completed, discontinued/withdrew) will be summarized both by treatment group and overall. Reasons for discontinuation/withdrawal will be presented.

An exploratory, per protocol (PP) analysis will focus on patients who use the assigned intervention on at least 50% of days during the first 30-day period. Usage meta-data on the headsets will facilitate sample definition in this population.

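### Headset-related adverse event percentages are taken over all randomised participants, including those who never used the headset, and so understate the rate among users by the never-user share

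*Protocol*

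**What the plan says.** Both documents name one population for everything. Protocol section 9.3 reads "All efficacy and safety data summaries and analyses will be performed by study arm using an Intent-to-Treat (ITT) population defined as all randomized patients", and SAP section 4.2 uses the same words: "All efficacy and safety data summaries and analyses will be performed by study arm using an Intent-to-Treat (ITT) population". On safety itself, protocol section 9.4.4 adds only this, repeated in SAP section 4.7: "All safety analyses will be descriptive. No statistical testing will be performed". Section 9.4.1 sets the format: "Categorical variables will be summarized using the number and percentage of patients in each category". A safety result is therefore a count and a percentage of the randomised arm.

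The only other population is an exploratory per-protocol set, defined by use on at least half of the first 30 days. It is not assigned to safety. It would not serve as an exposed set either, because it drops anyone who tried the headset and soon stopped.

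The protocol also expects some randomised participants to remain unexposed. Under section 7.2, those who leave "without engaging with the VR intervention will be replaced". The same section defines engagement as any self-reported use or any metadata on the headset. Section 7.3 adds people who receive the device and do not arrange the onboarding call within 30 days. Neither section takes these people out of the set of all randomised patients.

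**The concern.** The events the protocol expects from the intervention (cybersickness, neck pain, a rash from the facial interface; section 8.3.1) need the headset to be worn. The routine event question in section 8.3.4 asks only about unpleasant experiences that the participant attributes to using it. A never-user adds one to the denominator and cannot add to the numerator.

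Protocol section 2.2 describes the long-term safety and tolerability of therapeutic VR as largely untested and commits the study to assessing it. No safety test is planned, so the descriptive percentages are the whole safety result. A reader will naturally take them as the chance of a side effect for someone who uses the device, which is not what a percentage of all randomised participants estimates.

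**Working it through.** **The plan's own figure.** Neither document states an expected safety rate, a never-user count or a safety denominator, so there is no safety figure to reproduce. The main design figure, 83% power for either VR arm against sham, does reproduce: 83.3% in 100,000 simulated three-arm trials with 120 per arm, a 5-point difference, SD of change √200 = 14.14 and two-sided 0.025 per comparison. It has no bearing on this point.

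**Inputs.**
- Rate among users, r: up to one in four for cybersickness (protocol 8.3.1), so 25% as an upper value. Values of 10% and 5% are added for illustration.
- Never-user share of those randomised, u: not given. Assumed range 2% to 10%.
- Proxy for the top of that range: protocol 11.3 says that "certain participants are eligible for replacement if they are withdrawn after randomization" and expects half of the 360 to be reached at about participant 200. Half of 360 is 180; 200 − 180 = 20; 20 / 200 = 10%.

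**Formula.** With N randomised in an arm, (1 − u)N are users and r(1 − u)N of them have the event.
- Reported percentage: r(1 − u)N / N = r(1 − u)
- Absolute shortfall: r − r(1 − u) = ru
- Relative shortfall: ru / r = u

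**Results (reported percentage).**

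| Rate among users | u = 2% | u = 5% | u = 10% |
|---|---|---|---|
| 25% | 24.5% | 23.75% | 22.5% |
| 10% | 9.8% | 9.5% | 9.0% |
| 5% | 4.9% | 4.75% | 4.5% |

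The shortfall at 25% is 0.5, 1.25 and 2.5 points.

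**Check by counts.** If 120 users in an arm have 30 events, the rate is 30 / 120 = 25%. If those users are 90% of the randomised, the arm has 120 / 0.9 = 133.3 randomised, and 30 / 133.3 = 22.5%.

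**Between arms.** With the same u in two arms, the ratio of reported rates is r₁(1 − u) / [r₂(1 − u)] = r₁ / r₂, unchanged. The difference is (1 − u)(r₁ − r₂), shrunk by the factor 1 − u.

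**How good the 10% proxy is.** Section 14 dates the recruitment supplement to version 6 (November 2021). Replacement was narrowed to people who had not used VR in version 6.4 (July 2023). The roughly 20 replacements may therefore include people who did use the headset, so 10% may overstate u. Participant 200 is also a rounded projection. In the other direction, never-users who do not formally withdraw would not be in that count.

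**The case against.** The other side has several good points.

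- **Size.** The effect is small, u is unknown, and 25% and 10% are both high-end inputs. No safety endpoint appears in the objectives tables and no decision uses this denominator. This stands, and it limits the weight of the point.
- **Scope.** Cybersickness is also measured with the Simulator Sickness Questionnaire at Day 1. A non-completer has no score, not a score of zero, so those summaries are not diluted. This stands; the point is confined to adverse event percentages.
- **Risk of the remedy.** Adverse events are defined regardless of relatedness (8.3.1) and recorded from consent onward (8.3.4). Section 2.3.1 lists distress from questionnaire items, which a non-user can have. Dropping the all-randomised table would lose such events. This stands, and the fix keeps that table.

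Three stronger inferences are tempting, and the documents do not support them.

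- **That participants who never answer an event assessment are counted as event-free.** Neither document says so. SAP 6.1 excludes further imputation in descriptive analyses, which fits treating them as missing at least as well. Nor are surveys said to be the only source of events: 8.3.4 says events may come to attention through the assessments, 8.2 lists other monitoring, and 8.2.1 gives every participant a support line.
- **That the understatement differs between arms.** All arms receive the same headset and participants are blinded. Nothing in the documents indicates unequal non-use.
- **That replaced non-engagers already fall outside the analysis.** The amendment rationale for the replacement rule could be read that way, but the operative text of 9.3 and SAP 4.2 says all randomised.

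**Conclusion.** The point holds for percentages of headset-related adverse events. Relative to the rate among users, they are understated by exactly the never-user share. The direction is certain whenever u is above zero, provided the tables follow the text and divide by all randomised patients. The size is modest: 0.5 to 2.5 points on a 25% rate for u between 2% and 10%. That range is an assumption, with 10% as an upper-end proxy rather than an observed never-user rate. Ratios between arms are unaffected if non-use is equal. The efficacy analysis and the use of ITT for it are not in question. The change is worth making because these percentages are the trial's only safety output and the remedy uses definitions and data already in the plan.

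**What to change.** In protocol 9.3 and SAP 4.2:

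1. Add a safety set: randomised participants with any VR engagement, by the existing section 7.2 definition (any headset metadata or any self-reported use), analysed by program received.
2. Make this set the main denominator for headset-related adverse event rates, reported as n/N by arm.
3. Report beside it, by arm, the number who completed at least one event assessment, so that readers can see how many had the chance to report an event.
4. Keep the all-randomised adverse event table as supportive, so that events from consent onward and events in non-users are still shown.
5. Keep ITT for efficacy. State explicitly that participants replaced under section 7.2 remain in the all-randomised set, if that is the intention.

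The cost is a wording change in both documents, one flag variable and one extra table. Headset metadata and self-reported use are already collected. Grouping by program received will match the randomised grouping unless a headset was misassigned, which nothing in the documents suggests; it is a convention that costs nothing.

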### 9.4 STATISTICAL ANALYSES

#### 9.4.1 GENERAL APPROACH

All statistical analyses will be performed jointly by the Cedars-Sinai Biostatistics Core and the Cedars-Sinai Center for Outcomes Research and Education (CS\_CORE) using SAS® software version 9.3 or higher (SAS Institute, Cary, NC, USA), R pack3.5.0 (R Foundation for Statistical Computing, Vienna, Austria) or Stata software version 14 or higher (StataCorp LLC, College Station, TX, USA).

Continuous variables will be summarized using descriptive statistics (N, mean, standard deviation, minimum, median, and maximum). Categorical variables will be summarized using the number and percentage of patients in each category. Data will be summarized with respect to patient demographic and baseline characteristics both across the study and by study-arm. The efficacy endpoints, safety assessments, and other outcome results for each treatment group will be summarized descriptively unless otherwise indicated. In addition, statistical model estimates of least squares means, treatment differences, p-values and 95% confidence intervals will also be provided where relevant. The fit of linear models will be assessed using residual plots and/or other diagnostic plots as appropriate. The fit of logistic models will be assessed using Hosmer-Lemeshow goodness-of-fit and/or receiver operating characteristic (ROC) curves as appropriate. All statistical tests will be 2-sided and performed at the 0.05 level of significance unless stated otherwise. Baseline is defined as the value at the screening week (Day -8 to Day -2) for all parameters, unless specified otherwise.

#### 9.4.2 ANALYSIS OF THE PRIMARY EFFICACY ENDPOINT(S)

The goal of this analysis is to test the effectiveness of immersive VR in improving measures of pain interference. The trial will be a success if there is statistical evidence that either immersive VR group is better than sham VR.

The primary efficacy endpoint is the change from study baseline to Day 30 in pain interference as measured by PROMIS-PI t-score. The primary analysis will compare each treatment group separately to the control group using a linear mixed model repeated measures (MMRM) analysis. The repeated measures are the change from baseline PROMIS-PI t-score obtained at Days 7, 15, and 21, respectively. The model will include fixed categorical effects for treatment, week, treatment by week interaction, and the baseline PROMIS-PI t-score as a continuous covariate. We will employ the Stata *xtmixed* command

with restricted maximum likelihood estimation (REML) and an unstructured within-patient covariance structure for this model. We will evaluate the assumptions of the model, including normality, using residual and other diagnostic plots of model fit.

From this model, we will estimate least squares means, standard errors, treatment differences in least squares means, and 95% confidence intervals for each time period. Primary inference will be based on the treatment comparison of least squares means for Day 30, and a p-value will be presented for this time period only. The null hypothesis is that the mean difference in the primary endpoint between the treatment groups and the sham control group is zero, versus the alternative hypothesis that these differences are not zero. The hypotheses can be expressed as follows:

$$H0_a: \mu_{SB} - \mu_{control} = 0 \text{ versus } H1_a: \mu_{SB} - \mu_{control} \neq 0$$

$$H0_b: \mu_D - \mu_{control} = 0 \text{ versus } H1_b: \mu_D - \mu_{control} \neq 0$$

Where  $\mu_{SB}$  refers to the mean change from baseline to Day 30 in Promis-PI t-score in the Skills-based VR treatment group,  $\mu_{control}$  refers to the mean change from baseline to Visit Day 30 in Promis-PI t-score in the sham treatment group, and  $\mu_D$  refers to the mean change from baseline to Day 30 in Promis-PI t-score in the Distraction VR treatment group. The test will be performed using the final MMRM model with a two-sided significance level of 5%. Estimated least squares means for change from baseline and the observed absolute values ( $\pm$  SE) by treatment group will be plotted over time.

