### 6.3 MEASURES TO MINIMIZE BIAS: RANDOMIZATION AND BLINDING

We will allocate study participants using a random number generator to assign blocks of 3, 6, 9, or 12 to ensure there is an equal distribution in the EaseVRx skills-based group vs. the EaseVRx-Distraction group vs. the EaseVRx-Sham group. Participants, their clinical providers, and study statisticians will be blinded to the study arm. The groups will be labeled as A, B or C at random. A clinical research coordinator will ship the headset containing the assigned program to the participant and enter the group label into the log of enrolled participants. Datasets will be provided to the statistician using these group labels. The research coordinator who maintains the list of randomization assignments will not call participants on the telephone. Because the intervention is conducted in participants' homes and the data are collected remotely, the participants will not encounter each other and thus will be less likely to guess their study arm assignment. We anticipate there will be no circumstances during the study that require unblinding of an individual participant or a whole group because we do not expect any related SAEs to occur with this low risk intervention.

We have restructured the block randomization module within REDCap with stratification based on the 4 sites of recruitment (1 – pain clinic, 2 spine clinic, 3 – rheumatology clinic, 4 – Deep6). Randomization will be performed on a 1:1:1 basis across the 3 treatment groups and stratified across the 4 treatment sites with random block sizes (3, 6, 9, or 12). Allocation tables will be generated using STATA v16 software and uploaded into REDcap for patient allocation.

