#### *PCS SF-6*

The change from study baseline to Day 90 in pain catastrophizing as measured by PCS SF-6 is a secondary endpoint. This analysis will compare the treatment groups, separately, to the control group using a MMRM analysis. The repeated measures are the change from baseline PCS SF-6 score obtained for Day 15, 30, 60, and 90, respectively. The model will include fixed categorical effects for treatment, week, treatment by week interaction, and the baseline PCS SF-6 score as a continuous covariate. We will employ the Stata *xtmixed* command with REML and an unstructured within-patient covariance structure for this model. We will evaluate the assumptions of this model, including normality, using residual and other diagnostic plots of model fit.

From this model, we will estimate least squares means, standard errors, treatment differences in least squares means, and 95% confidence intervals for each time point. Primary inference will be based on the treatment comparison of least squares means for Day 90 from this model, and a p-value will be presented for this time period only. The null hypothesis is that the mean difference in the primary endpoint between the experimental arms and the sham arm is zero, versus the alternative hypothesis that this difference is not zero.

The change from study baseline to Day 90 in weekly MME of prescribed medication is a secondary endpoint. Descriptive summary statistics will be presented for weekly MME of prescribed medication at two timepoints: baseline and Day 90. Analysis of this endpoint will compare the difference in weekly MME of prescribed medication between the treatment groups and control group at baseline and Day 90 using analysis of covariance (ANCOVA), adjusting for baseline MME. We will assess the assumptions underpinning the ANCOVA model graphically and will undertake appropriate transformation of the weekly average MME outcome as deemed appropriate. If no suitable transformations can be found, bootstrapped confidence intervals for the between-group differences in weekly MME will be produced. Both adjusted and unadjusted between-group comparisons will be presented with 95% confidence intervals.

---

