#### 9.4.7 SUB-GROUP ANALYSES

Subgroup analyses are planned for the change from baseline in PROMIS-PI. An MMRM model will be used to test for treatment by subgroup interactions. Interactions with a significance level of less than 10% will be considered potentially important and flagged for further assessment. In general, the models will include fixed categorical effects for treatment, week, treatment by week interaction, subgroup, and treatment by subgroup interaction. The p-values of interaction terms will be presented, as well as the least squares means and 95% confidence intervals by treatment and subgroup classification factor. Descriptive statistics of the observed and change from baseline PROMIS-PI t-score will also be presented by treatment and week within each subgroup.

Subgroup analyses will be performed for the following subgroups:

- Dosage of VR (minutes per week)
- Previous experience with VR
- ITQ score
- Presence score
- Patient comorbidities
- History of spinal surgery
- Pain severity and duration
- Sociodemographics (i.e. age, sex, race, ethnicity, workers comp, marital status, education)
- Other treatments (see section 6.5)
- TAPS-1, TAPS-2
- Mood disturbances (e.g., current depressive disorder or not, severely depressed mood vs. non-depressed, etc.)
- Radicular vs. non-radicular back pain
- SSQ Cutoff (Score of >15)
- Treatment Expectation Question
- Perception of arm of study question
- Motion Sickness Propensity Survey

The primary MMRM models will be re-fit to include terms describing subgroups. The change from baseline PROMIS-PI score obtained at Day 30 will be compared between the treatment groups using MMRM analysis. The repeated measures are the change from baseline PROMIS-PI score obtained for Day 7, 15, 21, and 30, respectively. The model will include fixed categorical effects for treatment, week, treatment by week interaction, relevant subgroup, treatment by subgroup interaction, and the baseline PROMIS-PI score as a continuous covariate. The estimated least squares means and 95% confidence intervals on the treatment comparison for Day 7, 15, 21, and 30, will be presented in forest plots for each subgroup of relevance.

See Section 9.4.9 under exploratory analysis for more detail.

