#### *PGIC*

An exploratory endpoint is the change in disease severity as measured by the PGIC at Day 90. This secondary analysis will compare the treatment groups, separately, to the control group using a logistic regression analysis. Based on the PGIC assessment, a dichotomous scale of “Yes” or “No” will be derived. A favorable response of 5-7 on the PGIC indicates “Yes”, significant improvement occurred over the course of the study. An unfavorable response of 1-4 indicates “No”, significant improvement did not occur over the course of the study.

The percentage of patients in each treatment arm responding in the “Yes” and “No” categories will be compared to the percentage of patients in the control arm responding in the “Yes” and “No” categories via the Cochran Mantel-Haenszel test. We will analyze responder status (i.e. “Yes” vs “No” as the dependent variable) using logistic regression, with terms for study-arm and baseline PROMIS-PI.

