#### 4.6.3 Subgroup Analyses

Subgroup analyses are planned for the change from baseline in PROMIS-PI. An MMRM model will be used to test for treatment by subgroup interactions. Interactions with a significance level of less than 10% will be considered potentially important and flagged for further assessment. In general, the models will include fixed categorical effects for treatment, week, treatment by week interaction, subgroup, and treatment by subgroup interaction. The p-values of interaction terms will be presented, as well as the least squares means and 95% confidence intervals by treatment and subgroup classification factor. Descriptive statistics of the observed and change from baseline PROMIS-PI t-score will also be presented by treatment and week within each subgroup.

Subgroup analyses will be performed for the following subgroups:

- Dosage of VR (minutes per week)
- Previous experience with VR
- ITQ cutoff score
- Presence cutoff score
- Patient comorbidities
- History of spinal surgery
- Pain severity and duration cutoffs
- Socio-demographics (i.e. age, sex, race, ethnicity, marital status, zip code)
- Other Medications
- TAPS-1, TAPS-2

The primary MMRM models will be refit to include terms describing subgroups. The change from baseline PROMIS-PI score obtained for Day 30 will be compared between the treatment groups using MMRM analysis. The repeated measures are the change from baseline PROMIS-PI score obtained for Day 7, 15, 21, and 30, respectively. The model will include fixed categorical effects for treatment, week, treatment by week interaction, relevant subgroup, treatment by subgroup interaction, and the baseline PROMIS-PI score as a continuous covariate. The estimated least squares means and 95% confidence intervals on the treatment comparison for Day 7, 15, 21, and 30 will be presented in forest plots for each subgroup of relevance.

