## 6.4 Missing Data and Sensitivity Analyses

If the primary or key secondary endpoint is missing in >15% of patients in either treatment group, then the pattern of baseline covariates with missing values will be examined using the method of Little and in case the data is not missing completely at random, missing values will be imputed using fully conditional specification with the multivariate imputation by chained equations (MICE) algorithm under the missing at random (MAR) assumption. Fifty or so data sets will be generated and analyzed separately, and the results will be combined using the formula according to Van Buuren. Similar considerations will be applied to missing data on the dependent variable in a repeated measure mixed model by investigating patterns of missingness and presence of nonignorable missing response data.

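### Allocation is stratified by four recruitment sources, but no primary or secondary efficacy model includes that factor (minor)

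*Protocol*

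**What the plan says.** Protocol 6.3 describes 1:1:1 allocation, "stratified across the 4 treatment sites with random block sizes (3, 6, 9, or 12"). The strata are the pain clinic, the spine clinic, the rheumatology clinic and Deep6.

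The primary analysis is a repeated-measures mixed model. Protocol 9.4.2 and SAP 4.6.1 give the same list of terms: "The model will include fixed categorical effects for treatment, week, treatment by week interaction, and the baseline PROMIS-PI t-score as a continuous covariate". The secondary models for pain interference at Days 60 and 90, sleep disturbance, anxiety and catastrophizing (Protocol 9.4.3, SAP 4.6.2) have the same structure, each with its own baseline score. Opioid dose is compared at baseline and "Day 90 using analysis of covariance (ANCOVA), adjusting for baseline MME".

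Recruitment source is in none of these models and in neither subgroup list (Protocol 9.4.7, SAP Subgroup Analyses). Neither document promises a stratified analysis, so this is an omitted design factor and not a contradiction. The SAP's Randomization and Blinding section does not mention strata, but its text breaks off mid-sentence, so nothing is inferred from that.

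**The concern.** Stratified blocks force the arms to be balanced on recruitment source. If source predicts outcome, that balance makes the treatment difference less variable. A model without the factor leaves the between-source variation in its residual, so it does not see the gain: the reported standard error is larger than the true one, intervals are too wide and tests are conservative. The trial takes on the work of stratifying and gives up part of the return.

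The summary-of-changes entry that introduced stratification lists sections 6.3 and 9.4.7 but not 9.4.2 or 9.4.3. That suggests the efficacy models were not updated when the design changed. This is an inference; the documents do not say so.

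**Working it through.** **1. The plan's own figure.** Inputs from Protocol 9.2 and SAP 3.5: 120 per arm, a difference of 5 points, SD 10 at each time, correlation ρ = 0 between baseline and Day 30, two-sided 0.025 per comparison. SD of change = √(10² + 10²) = 14.14, and SE of a difference = 14.14 × √(2/120) = 1.826. Power for one comparison is 69.0%. Simulating 200,000 trials gives 83.3% power for at least one arm, against the stated 83%, and familywise error 0.047, against the stated 0.049 (within the Monte Carlo error of 10,000 replicates, about ±0.004). The stated power reproduces and does not depend on the stratum term.

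**2. Closed form for a baseline-adjusted Day 30 comparison, no dropout.** The residual SD is 10√(1 − ρ²), which is 10 at ρ = 0. Let R² be the share of residual variance explained by source. The documents give no value, so 0, 2, 5 and 10% are assumed.

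- Model SE without the factor: 10 × √(2/120) = 1.291. True SE under stratified allocation: 1.291 × √(1 − R²).
- SE overstatement: 1/√(1 − R²) − 1.
- True size of a nominal 5% test: 2[1 − Φ(1.96/√(1 − R²))].
- Power at 0.025 without the factor: Φ[(5 − 2.2414 × 1.291)/(1.291√(1 − R²))]. With it: Φ[5/(1.291√(1 − R²)) − 2.2414].

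| R² | SE overstated | True size at 5% | Power without | Power with |
|---|---|---|---|---|
| 0 | 0% | 5.0% | 94.86% | 94.86% |
| 2% | 1.0% | 4.8% | 95.03% | 95.26% |
| 5% | 2.6% | 4.4% | 95.29% | 95.84% |
| 10% | 5.4% | 3.9% | 95.73% | 96.72% |

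Worked line at R² = 10%: true SE = 1.291 × 0.9487 = 1.225. Without the factor, Φ[(5 − 2.894)/1.225] = Φ(1.720) = 0.957. With it, Φ(4.082 − 2.241) = Φ(1.841) = 0.967. At ρ = 0.5 and R² = 10% the change is from 99.06% to 99.33%, or 0.3 point.

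**3. Simulation of the four-visit model** (6,000 trials per setting, N = 360; Days 7, 15, 21 and 30; REML; unstructured covariance; stratified blocks of 3, 6, 9 or 12). Assumptions: ρ = 0, between-visit residual correlation 0.6, four equal strata in expectation, and 15% dropout completely at random by Day 30. The 15% is borrowed from the threshold in SAP 6.4 ("If the primary or key secondary endpoint is missing in >15% of patients in either treatment group").

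| R² | Day 30 SE, without / with | Per-arm power at 0.025, without / with |
|---|---|---|
| 0 | 1.353 / 1.353 | 92.7% / 92.6% |
| 2% | 1.354 / 1.341 | 92.6% / 92.9% |
| 5% | 1.350 / 1.318 | 93.1% / 94.0% |
| 10% | 1.349 / 1.284 | 92.6% / 94.1% |

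The Monte Carlo SE of each power figure is about 0.3 point; both models in a row were fitted to the same trials. At R² = 10%, size at 0.05 is 0.042 without the factor and 0.053 with it. Unequal strata (10/15/15/60%) give a similar gain, 93.57% to 94.95%. If the source effect builds up over the visits (25, 50, 75 and 100% of its Day 30 size), a main effect gains 1.1 points and a source-by-visit term 1.4.

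**4. On the plan's basis** (change scores, SD 14.14, success in either arm; 8,000 simulated trials): without → with the factor, power is 82.9 → 82.8% at R² = 0, 83.2 → 83.8% at 2%, 83.4 → 84.9% at 5% and 83.6 → 86.7% at 10%. Familywise error without the factor falls from 0.046 at R² = 0 to 0.041 at 5% and 0.035 at 10%; with it, the error stays at 0.046.

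**5. Unequal dropout by source** (single visit, R² = 10%, four equal strata with evenly spaced effects, all assumed). The source SD is √0.10 × 10 = 3.16, so the source effects are −4.24, −1.41, 1.41 and 4.24. With dropout of 5, 10, 20 and 25% by source in one arm and a flat 15% in the other, the first arm's mean shifts by (−4.24 × 0.95 − 1.41 × 0.90 + 1.41 × 0.80 + 4.24 × 0.75)/3.40 = −0.29 point.

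**The case against.** The strongest reply is that no harm is shown. The present test is valid, the planned power stands, and the gain depends on an R² that nobody has stated and that may be zero. The models already adjust for the baseline score, so only what source adds beyond it counts; at ρ = 0.5 the closed-form gain is at most 0.3 point. At R² of 0 or 2% the simulated power differences are no larger than the Monte Carlo error. All of that stands, and it is why the point is minor. It does not argue for leaving the factor out: if source is not prognostic, including it costs about 0.1 point.

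The size of the gain also depends on the basis. The per-arm figures in steps 2 and 3 follow the planned baseline-adjusted model, while step 4 uses the plan's change-score calculation and shows larger gains. Both are given so that neither is mistaken for the other.

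Unbiasedness needs a condition: step 5 shows a shift of about 0.3 point if dropout by source differs between arms. That is small, and it favours including the factor.

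Finally, the change is late. "Participants, their clinical providers, and study statisticians will be blinded to the study arm", but they receive data already separated into groups A, B and C, so their blinding is to the identity of the groups. The term should be fixed without looking at what it does to the comparisons.

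**Conclusion.** The concern holds as a minor one. Every primary and secondary efficacy model omits the factor by which allocation is stratified, and no reason is given. The consequence is at most conservatism: for an assumed R² of 0 to 10%, standard errors are overstated by 0 to 5.4% and up to 1.5 points of per-arm power are forgone in the four-visit model, or about 3 points for either-arm success on the plan's basis. These figures rest on the assumed R², SD 10, ρ = 0 and, in step 3, 15% dropout completely at random. No magnitude was worked out for the secondary endpoints.

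**What to change.** Before unblinding, add recruitment source (four levels) as a fixed effect to the primary model, the secondary repeated-measures models and the opioid-dose ANCOVA, in Protocol 9.4.2–9.4.3 and SAP 4.6.1–4.6.2. For opioid dose, say that the term belongs to the adjusted comparison.

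Carry the term into the subgroup analyses. Protocol 9.4.7 says "The primary MMRM models will be re-fit to include terms describing subgroups", and the SAP's Subgroup Analyses section spells out its own list, "The model will include fixed categorical effects for treatment, week, treatment by week interaction, relevant subgroup, treatment by subgroup interaction", which would otherwise no longer match the primary model.

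For consistency, add it to the exploratory models and name it as the stratum where the SAP compares PGIC "categories via the Cochran Mantel-Haenszel test", which at present has none. In the PGIC logistic regression the odds ratio then becomes conditional on source, and the text should say so. Bring the SAP's Randomization and Blinding section into line with Protocol 6.3.

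Editorial only, and separate from this point: Protocol 9.4.2 lists the repeated measures as Days 7, 15 and 21. Day 30 should be added to agree with Protocol 9.4.7 and SAP 4.6.1.

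The cost is three degrees of freedom per model and some wording. Source is already the stratification variable in REDCap, so no data need collecting. The Statement of Compliance requires IRB approval of the amendment. By the plan's dates it would come after randomization was due to end (9/5/2023 in Protocol 8.1; this revision is dated 19 October 2023), which is why it must be settled while the statisticians are still blinded.
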